The only survey of mental health supported accommodation to be carried out in England (led by co-investigator SP) found few differences in the characteristics of service users in different types of setting or in the support offered (Priebe et al., 2009). The survey sampled 12 nationally representative regions, identified a total of 481 projects of which 250 were randomly sampled. Of these, 153 responded to a postal survey; 57 were nursing/residential care homes (with a mean 16 residents), 61 were individual or shared flats with on-site staff support (with a mean 13 service users) and 30 provided floating outreach to a mean 34 service users in their own independent flats, usually rented from the Local Authority or a Housing Association. Staff provided anonymised data on 414 service users. The majority were male, 80% had a diagnosis of a psychotic disorder and 48% also had a substance misuse history. There were no differences in service user characteristics between service types. Around 40% of those in supported housing or receiving floating outreach were participating in some form of community activity (compared to 25% of those in residential care) but similar numbers of hours were spent by service users across all settings in education or work (mean 13 hours per week) and only 3% were in open employment. Staff made contact with users on average six days a week in supported housing and four days a week in floating outreach services. Between four and six service users (18-25%) moved on from each service annually. Although residential care settings had a higher proportion of trained mental health staff than the other services, almost all service users in all types of setting were prescribed medication and all services provided support with personal care and activities of daily living. The costs of these services appeared to be driven by the local tradition of provision rather than clinical need. Shepherd and Macpherson (2011) have also commented that the development of local supported accommodation provision appears to be largely determined by history, the sociodemographic context of the area and the support available from primary care and secondary mental health services.

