We recently carried out a qualitative study of staff and service users of supported accommodation services across England and found few differences in the overall aims and type of support provided by supported housing and floating outreach services. Staff of both types of service reported that they aimed to support service users to maintain and increase their confidence and skills in order to achieve the highest level of independent living in the community. They reported that they achieved this through prompting and supporting service users to practice and gain confidence with these skills incrementally to the point where they could manage them independently. Staff of both types of service reported providing support with activities of daily living (self-care, laundry, housework, shopping, cooking, paying bills and managing finances), managing medication, community activities, keeping appointments and managing risk and safety (Sandhu et al, paper in preparation).

Although these previous studies do not suggest that there are major differences between the content of care provided in supported housing and floating outreach services, most areas of the UK have supported accommodation systems where service users move to more independent settings as their skills improve (from residential care to supported housing and from supported housing to floating outreach). This allows for graduated “testing” but many users dislike repeated moves. Recently, there has been increased investment in supported flats rather than group settings since many service users prefer their own independent living space (Tanzman, 1993; Massey and Wu, 1993). A number of studies have identified discrepancies between service user and staff views on the level of support required, with service users tending to prefer more independent accommodation (Minsky et al., 1995; Piat et al., 2008). Family members also tend to prefer their relatives move to staffed environments (Friedrich et al., 1999). An important criticism of staffed settings is the maintenance of institutional regimes and impaired facilitation of service users’ autonomy through over support and a poor rehabilitative culture (Ryan et al., 2004). Conversely, some service users and family members have reported that independent tenancies are socially isolating (Ryan et al., 2004; Walker et al., 2002).

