each service leaving vacancies for 200 new referrals per year across the three sites. We aim to recruit and randomise 60 participants from across the three sites and have allowed 15 months for recruitment. A main aim of the feasibility trial is to establish whether randomisation to different types of supported accommodation is possible, including its acceptability to service users, clinicians and service providers and its feasibility given the complex logistics involved. A relevant comparison here is with the "Individual, Place and Support" model of supported employment. Though originally considered too logistically challenging for evaluation through randomised controlled trials, such trials have now been carried out successfully (Crowther et al., 2001; Twamley et al, 2003; Burns et al., 2008). Similar challenges may apply here. Service users do not necessarily have much control over the type of supported accommodation they are referred to. Clinicians and providers tend to steer the process and may be anxious about a service user's suitability for one of the two types of supported accommodation we propose to compare. This is not a unique problem in that professionals and clinicians often have opinions that are not evidence based about what is best for their patients. However, we will need to engage with key individuals in each region to agree acceptable protocols. Where there is agreement for a participant to be randomised and they have given their informed consent, they will be randomly allocated on an equal basis to either the supported housing service or the floating outreach service. Randomisation will be conducted independently of the research team by a statistician from the Pragmatic Clinical Trials Unit based at Queen Mary's University London. Randomisation will be stratified by site to ensure equal numbers of participants are allocated to both types of service within and across sites.

COMPARISON SERVICES

Supported housing services provide a constant level of staffing on-site to a number of service users living in individual or shared tenancies with the expectation of move-on within two years. Floating outreach services provide support of flexible intensity to service users living in an independent tenancy which is time-unlimited. Current evidence does not suggest that there are major differences in the content of care and support provided by these two supported accommodation models.

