- Engagement in community activities - proforma (leisure, education and employment activities) and **Time Use Diary*** [Jolley et al., 2006]
- Social inclusion (**SIX*** [Priebe et al., 2008] plus items from **Manchester Short Assessment of Quality of Life*** [Priebe et al., 1999] such as friendships and relationships with family)
- Costs of care (**Client Service Receipt Inventory*** [Beecham and Knapp, 1999]) – this includes details of staff contacts, hospital admissions, outpatient and other contacts with health services.
- Satisfaction with service (**Client Assessment of Treatment** [Priebe et al., 1995])
- Engagement with services/therapeutic alliance (**Scale to Assess Therapeutic Relationships in Community Mental Health Care** [McGuire-Snieckus et al, 2007])
- Service user attitude towards moving on successfully (single question “I expect to become more independent in the next two years)

We estimate the service user interview will take around 30 minutes.

From case notes and interviews with key staff:

- Number and length of any **hospital admissions** (including those for mental health and physical health problems)
- Indicators of community placement breakdown (**eviction notice or loss of tenancy**)
- Indicators of difficulty managing the tenancy (**rent, service charge or other bill arrears, recorded complaints from neighbours**)
- Evidence of greater independence (**for those in supported housing, move on to less supported accommodation without placement breakdown or hospital admission; for those in floating outreach, managing with less support without loss of tenancy or hospital admission**)
- Staff attitudes towards service user moving on successfully (single question “I expect this person to become more independent in the next 12 months”)
- Activities of Daily Living (staff rated **Life Skills Profile*** [Parker et al., 1991])
- Details of current prescribed medication (one item from **Client Service Receipt Inventory*** [Beecham and Knapp, 1999])
- Medication adherence (two items from **Life Skills Profile***; **Compliance Scale*** [Heyward et al., 1995])
- Mental health and social functioning (**Health of the Nation Outcome Scale*** [Stein, 1999])
- Engagement in community activities - proforma and **Time Use Diary*** [Jolley et al., 2006]

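### Arrears and neighbour complaints are taken only from case notes and staff of the allocated service, so they may be detected unequally between the arms

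*Protocol*

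**What the plan says.** In the Protocol, section 12 month outcome assessment, difficulty managing the tenancy is indicated by "rent, service charge or other bill arrears, recorded complaints from neighbours". The item stands in the list headed "From case notes and interviews with key staff". Eviction notice and loss of tenancy are in the same list, as a separate indicator of placement breakdown. The list for the service user interview has no question on any of these. No other section names a landlord or housing-office record.

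The two models are staffed differently. Under Comparison Services: "Supported housing services provide a constant level of staffing on-site to a number of service users living in individual or shared tenancies". For the other arm: "Floating outreach services provide support of flexible intensity to service users living in an independent tenancy which is time-unlimited". The Background section, reporting an earlier national survey, says that floating outreach users lived "in their own independent flats, usually rented from the Local Authority or a Housing Association". It also says: "Staff made contact with users on average six days a week in supported housing and four days a week in floating outreach services". The same section reports, from a qualitative study, that staff of both models give support with "paying bills and managing finances".

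Outcome quality is judged numerically by missing data alone. An outcome with more than 30% missing is treated as unfeasible for a larger trial. Between 10% and 30%, the team will look for ways to raise the response. Under Masking of Researchers, the Protocol accepts that assessors may be unmasked, partly because it regards many outcomes as objective and free of rater bias.

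**The concern.** The informant for this outcome is part of the intervention being compared. A worker who is on site throughout can see or hear of a complaint or an unpaid charge in a way that a visiting worker may not. If so, the same event could have a different chance of being recorded depending on the arm, even though the data form and the rater's honesty are the same. That is a detection problem, and calling the outcome objective does not remove it.

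Sustaining a tenancy is a natural measure of success for these services, and choosing appropriate outcomes for a large trial is a stated output of this study. An outcome with arm-dependent detection could pass the missing-data thresholds with almost complete data and be carried into the main trial. There, a difference in recording could be read as a difference in how well people manage their tenancies.

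**Working it through.** The Protocol states no event rate, effect size or detection rate for this outcome, so there is no figure to reproduce. The check is a reading of the text followed by an illustration on stated assumptions.

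**Reading**

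1. *Source.* Case notes and key staff are the only listed sources for arrears and complaints. Elsewhere the Protocol uses two sources. Under Comparison Services, staff contacts are collected from users and corroborated with staff and case notes, and the Time Use Diary is completed separately by user and staff.
2. *Opportunity to observe.* Staffing is constant and on site in one arm, flexible and visiting in the other. The earlier survey gives six against four contact days a week. The difference is real but not extreme.
3. *Evidence the other way.* Staff of both models help with bills, which is a direct route to knowing about arrears.
4. *What is not stated.* The Protocol does not say who the landlord is in supported housing, whether its staff hold rent or complaint records, or how an event unknown to staff is coded.

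**Illustration**

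Assumptions, none from the documents: the true rate p is the same in both arms, at 20% to 40%; supported housing detects 90%; floating outreach detects a share d of 50% to 90%.

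Recorded rate = p × share detected. With p = 30%, supported housing records 0.30 × 0.90 = 27%. For floating outreach:

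| d | Recorded rate | Artefactual difference |
|---|---|---|
| 90% | 27% | 0 points |
| 80% | 24% | 3 points |
| 70% | 21% | 6 points |
| 60% | 18% | 9 points |
| 50% | 15% | 12 points |

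At d = 50% the difference is 0.20 × (0.90 − 0.50) = 8 points for p = 20%, and 0.40 × (0.90 − 0.50) = 16 points for p = 40%. The whole grid therefore runs from 0 to 16 points.

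**Could the arm comparison in this trial reveal it?**

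Sixty participants allocated equally give 30 per arm; complete follow-up is assumed. The 95% half-width is 1.96 × √[a(1 − a)/30 + b(1 − b)/30], where a and b are the recorded rates. For 27% and 18% this is 1.96 × √[(0.1971 + 0.1476)/30] = 21 points. Across the grid it runs from 17 to 24 points. Comparing the arms in this trial could neither show nor exclude a bias of this size.

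**Could it matter in a full trial?**

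The standard two-proportion formula (two-sided 5%, power 80%) is n = [1.96 × √(2m(1 − m)) + 0.842 × √(a(1 − a) + b(1 − b))]² / (a − b)², with m the mean of a and b. With a = 0.27, b = 0.18 and m = 0.225, n = (1.96 × 0.5906 + 0.842 × 0.5871)² / 0.0081 = 337 per arm. At that size, detection of 90% against 60% would give an 80% chance of declaring a difference that does not exist. With equal detection there is no artefact at any size.

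**The case against.** A reader might infer a stronger claim: that floating outreach users rent from an outside landlord, so their tenancy problems will be under-counted and the comparison will favour floating outreach. The documents do not support that, for these reasons.

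- The statement about landlords describes the earlier survey, not the trial sites. It does not say that the landlord is separate from the support provider, and the Background section names housing associations among the providers of supported accommodation.
- The landlord in supported housing is not described, so a contrast in access to rent and complaint records is not shown.
- Help with bills in both models, and four contact days a week in floating outreach, make it likely that many problems would reach visiting staff.
- Loss of tenancy would be hard for a service supporting the person in that home to miss, so it should not be grouped with arrears and complaints.
- The coding of unknown events is not given. If a staff answer of not knowing were recorded as missing, the thresholds would apply.

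Little in this study rests on the item. The analysis is mainly descriptive, the stated feasibility criterion is recruiting the target of 60, and the trial exists partly to test whether such outcomes can be collected.

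All of this stands against the claim of a certain bias with a known direction. It does not answer the narrower point. The only source sits within the allocated service, its opportunity to observe differs by arm, and the Protocol plans no check that would show whether this matters.

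**Conclusion.** The concern holds in a limited form. Arrears and recorded neighbour complaints may be detected unequally between the arms, and the missing-data rule may not reveal it. Neither the existence nor the size of a bias is established. Under the assumed detection rates the artefact is 0 to 12 points at a 30% true rate, and 0 to 16 points over true rates of 20% to 40%. The zero is a real possibility. The conclusion takes key staff to be mainly workers of the allocated service; the Protocol does not define the term further for this list.

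This does not undermine the study's feasibility aim, since no primary outcome or sample size depends on it. It is a worthwhile, inexpensive improvement, best made now because this study is meant to inform which outcomes a main trial should use.

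**What to change.** Add a few direct questions on arrears, neighbour complaints and eviction notices to the 12-month service user interview, worded identically in both arms. Keep the case-note and staff items. Report agreement between the user source and the staff or case-note source separately by arm, as a feasibility result, before carrying this outcome into a main trial. This is the two-source approach already used for staff contacts and the Time Use Diary. It would also help to state how an event unknown to staff is coded, so that it can be told apart from a confirmed absence.

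The cost is a few minutes added to a service user interview estimated at about 30 minutes.

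Landlord records should be optional. They require disclosure by a third party, and the consent described under Likely Rate of Loss to Follow-up is framed around case notes and staff-rated measures. They should not feed a rule that counts an event if either source reports it, unless the records are similarly available in both arms. Otherwise non-response by landlords could introduce a new arm-dependent difference in detection.

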We will ask those who are recruited whether they have any preference for either of the two models (and if so, which) at baseline. We will also ask the referring clinician if they have any preference for the type of supported accommodation their client receives as part of the staff baseline interview. We will ask the service user and their care coordinator/keyworker to give their feedback about their experiences of randomisation and views about the trial using a simple proforma which will be included in the 12 month follow-up interviews. In addition, we will ask other key individuals involved in the supported accommodation referral process to give their feedback using the same proforma.

We will ask service users who do not wish to be randomised (and clinicians who do not agree for their service users to participate) their reasons for this. We will invite up to 60 service users in this group to participate in a naturalistic follow-up to determine their outcomes over time. If they are willing, we will collect the same baseline and outcome data as for randomised participants from staff and service users.

Baseline assessment

Before randomisation we will collect data on participants' age, gender, ethnic group, diagnosis, length of contact with mental health services and previous type of accommodation from staff and case notes. We will also assess their social function using the staff rated Life Skills Profile (Parker et al., 1991) and adjust for this in our analyses.

12 month outcome assessment

We will test the feasibility of collecting the following outcomes for service user participants at 12 months follow-up. These outcomes include those suggested by staff and service users in our previous qualitative study and those suggested in the background section of this protocol. Where relevant, assessments will be carried out at baseline as well as 12 month follow-up (denoted by *) in order to assess for baseline scores and adjust for these in our analyses. Where we have more than 30% missing data we will consider that outcome to be unfeasible to include in a larger trial. If there is more than 10% missing data for any outcome (but less than 30%) we will consider if there are ways to improve the response rate.

From service user interviews:

- Mental health (**Brief Psychiatric Rating Scale*** [Overall and Gorham, 1962])
- Quality of Life (**Manchester Short Assessment of Quality of Life*** [Priebe et al., 1999])

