Service use in the period before follow-up will be measured using the CSRI (Beecham and Knapp, 1999) and combined with unit costs. The service costs will be derived from expenditure data. Cost-effectiveness of the two types of service will be assessed by combining service costs with the composite outcomes described above. We will also use the SF36 (Ware et al., 1996) and EQ5D (Williams, 1995) to derive QALYs. The use of both is appropriate because there are concerns about using the EQ5D in this population (McCrone et al., 2009). The SF36 and EQ5D will be collected from service users at baseline and 12-month follow-up.

The relationship between EQ5D and SF36 (via the SF6D) QALYs and the other outcome measures will be examined. Uncertainty around the cost-effectiveness

estimate will be assessed using planes and cost-effectiveness acceptability curves and will depend ultimately on which primary outcome(s) is chosen.

OUTPUTS

Assessment of feasibility, required sample size and appropriate outcomes for a large scale randomised trial of two supported accommodation models.

TIMEFRAME

Month 31-44. Recruitment and baseline data collection

Month 31-40. Qualitative interviews with staff and service users

Month 41-54. Follow-up data gathered 12 months after randomisation

Month 55-60. Data cleaning, analysis and write-up

FINANCE

The Quality and Effectiveness of Supported Tenancies for People with Mental Health Problems (QuEST) Project is funded by the National Institute for Health Research Programme Grants Scheme in the amount of £1,642,079. The award will be administered by Camden and Islington NHS Foundation Trust.

COMPLAINTS

In the event of a complaint about the conduct of the study, the complaints should be reported immediately to the JRO [contact] who decide which complaints policy applies and who will be the lead organisation. The NHS complaints policy can only apply where the research subject is recruited through an NHS Trust. In other circumstances the UCL complaints policy will apply.

INDEMNITY

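### The independence outcome uses different success and disqualifying events for the two services, so a between-arm difference in it cannot be read as a treatment effect or used to size the main trial

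*Protocol*

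**What the plan says.** The protocol (12 month outcome assessment, list from case notes and key staff) defines *evidence of greater independence* in two halves:

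- Supported housing: "for those in supported housing, move on to less supported accommodation without placement breakdown or hospital admission".
- Floating outreach: "for those in floating outreach, managing with less support without loss of tenancy or hospital admission".

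Two lines earlier the same list explains placement breakdown: "Indicators of community placement breakdown (eviction notice or loss of tenancy").

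Comparison Services describes supported housing as offered "with the expectation of move-on within two years". For the other model it says: "Floating outreach services provide support of flexible intensity to service users living in an independent tenancy which is time-unlimited". The Timeframe section counts the 12 months from randomisation.

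The purpose at this stage is modest: "We will test the feasibility of collecting the following outcomes for service user participants at 12 months follow-up". The estimates are nevertheless meant to be used. Statistical Analysis says that their confidence intervals will help with power and sample size for a full trial. Outputs promises a sample size and suitable outcomes for that trial. Cost Effectiveness plans on "combining service costs with the composite outcomes described above".

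**The concern.** A single outcome name covers two different events. In supported housing a participant succeeds only by completing a move. In floating outreach a participant succeeds through a reduction in support that has no stated amount, instrument or reference time. The two proportions do not estimate the same quantity, so their difference mixes any real effect of the service model with the effect of the definition.

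The planned screen would not catch this. The protocol's stated test for dropping an outcome is more than 30% missing data. This item comes from case notes and staff, which the protocol expects to have even when a service user cannot be reached. It could pass the screen and go forward to the main trial although the arms are not comparable on it.

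The wording also leaves open whether being in a service means allocated to it or living in it. Outcome Assessments foresees people who decline to move to the allocated service. If the word means living in it, someone who entered neither service fits neither half.

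**Working it through.** **The two halves side by side**

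| | Supported housing | Floating outreach |
|---|---|---|
| Success event | Completed move to a less supported setting | Reduced support; no move needed |
| Amount and reference time | Fixed by the move | None stated |
| Disqualifying events | Placement breakdown (eviction notice or lost tenancy); admission | Lost tenancy; admission |
| Service horizon | Move-on expected inside two years | No time limit |
| Time of reading | 12 months | 12 months |

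**The same situation, scored by each half**

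1. A person needs less help but is at the same address. Supported housing: failure. Floating outreach: success.
2. A person lives in an independent tenancy with floating outreach at an unchanged level. Someone who came there from supported housing (the usual step, according to Background) is a success. Someone allocated there from the start is a failure.
3. A person is served an eviction notice, keeps the tenancy and otherwise meets the rule. Supported housing: disqualified. Floating outreach: not disqualified.

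Situations 1 and 3 lean towards floating outreach, and situation 2 leans towards supported housing. The text alone does not settle the net direction.

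**What the documents' figures allow**

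The plan's one related calculation reproduces: 20% annual move-on x 1000 service users = 200 vacancies a year.

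Sixty participants allocated equally give 30 per arm. The survey in Background reports: "Between four and six service users (18-25%) moved on from each service annually". Taken as a stand-in for supported housing, before removing anyone with a breakdown or admission:

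- 30 x 0.18 = 5.4
- 30 x 0.20 = 6.0
- 30 x 0.25 = 7.5

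The wait to move in is a feasibility outcome with no planning value. Assume a wait of d months and a constant hazard, so that the 12-month proportion is 1 - (1 - p)^((12 - d)/12). At p = 0.20:

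- d = 2: 1 - 0.80^(10/12) = 17.0%
- d = 4: 1 - 0.80^(8/12) = 13.8%

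Across p from 18% to 25% and d from 0 to 4 months, the range is 12.4% to 25%.

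No floating outreach rate is given. Hold supported housing at 20% and assume a range for the other arm. The protocol states no error rates for this item, so two-sided 5% and 80% power are assumed:

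n per arm = [1.96 x sqrt(2 x pbar x (1 - pbar)) + 0.8416 x sqrt(p1(1 - p1) + p2(1 - p2))]^2 / (p1 - p2)^2

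For 20% against 40%, pbar = 0.30 and n = (1.270 + 0.532)^2 / 0.04 = 81.2, rounded up to 82.

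| Assumed floating outreach rate | Difference (floating outreach minus supported housing) | n per arm |
|---|---|---|
| 10% | -10 points | 199 |
| 20% | 0 | undefined |
| 30% | +10 points | 294 |
| 40% | +20 points | 82 |
| 50% | +30 points | 39 |

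Both the sign of the difference and the sample size turn on how reduced support is scored, which the protocol leaves open.

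**The case against.** The best defence is the role of the item. It is one of a long list being tested for ease of collection. Success of the study is defined by recruiting 60 people in 15 months, and the analysis is mainly descriptive. Joint modelling is exploratory and limited to three outcomes, and this item is not named among them. No sentence ties the main-trial sample size to it. All of this stands and lowers the severity. It does not make the item comparable between arms, and nothing in the protocol keeps it out of the estimates that feed the main trial.

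The service-based wording also has a practical reason. Up to 60 non-randomised people are to be followed with the same data, and they have no allocated arm. The wording may equally mean allocated service. That calls for clarification and does not show that the trial will be analysed by service occupied.

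A reader might infer that the definition builds in an advantage for floating outreach of a predictable size. The documents do not support this. They give no success rate for floating outreach, and situation 2 above leans the other way. The move-on figures pool service types, so they do not cap the supported housing rate. The wait before moving in can affect either arm. A real effect could also contribute to any difference.

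A reader might also take the composite outcomes in Cost Effectiveness to mean this item. That is not secure, because social inclusion and risk are also assembled from several sources.

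**Conclusion.** The point holds, at moderate severity. The success events and the disqualifying events differ by service, so a between-arm difference in this item is confounded by its definition. It should not be read as a treatment effect or used to size a main trial. This follows from the protocol's wording and needs no numerical assumption, except that the eviction-notice difference takes placement breakdown to mean what the same list says it means.

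Neither the direction nor the size of the distortion can be established. The range from -10 to +30 points illustrates how unstable the comparison is and does not estimate bias. It rests on a pooled move-on rate used as a stand-in for supported housing and on assumed floating outreach rates. No corrected figure can be computed, because the documents give no rate under a common definition.

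**What to change.** 1. Report the two items as service-specific descriptions only. State that they are excluded from between-arm estimates, the joint model, cost-effectiveness and sample-size planning.
2. Use the same disqualifying events in both: eviction notice, lost tenancy or hospital admission, each counted since randomisation.
3. Classify randomised participants by allocated arm and keep those who never moved in within the denominator. Use service received only for the non-randomised naturalistic group.
4. For a between-arm comparison of independence, name a measure already collected identically in both arms at baseline and 12 months, such as the Life Skills Profile, adjusted for baseline as already planned. A reduction in staff contacts is a weaker choice. Contact depends on the service model (six days a week in supported housing against four in floating outreach in the survey), and the contacts proforma is completed only at 6 and 12 months.
5. In Cost Effectiveness, replace the reference to composite outcomes with the QALYs already planned and the named common outcome or outcomes. This also agrees with the stated aim, at the end of the outcome section, of keeping outcomes distinct in the joint model.

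The cost is protocol wording; no new data collection is needed. The trial gives up a single headline comparison of move-on. The Life Skills Profile is staff rated, may be collected unmasked, and measures functioning rather than the support a person receives.
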